### 5.7.2. Analysis of Primary Efficacy Variables

The change in the SDI score at week 10 from baseline will be analyzed in the full analysis set (FAS) using multiple imputation (MI), with an analysis of covariance (ANCOVA) model with treatment group as fixed effect, and the baseline SDI value as continuous covariate. (primary approach).

Due to the substantial imbalance at baseline in the number of patients in the two randomization strata (only 12.8% patients in the strata of baseline SDI  $> 7$ ), the multiple imputation and ANCOVA model will not use randomization strata as a factor.

Patients' efficacy data through week 12 after rescue medication usage will be set to missing first, and then be imputed by the MI method.

Missing data from the FAS will be imputed 50 times to generate 50 complete data sets by using the SAS procedure MI following the 2 steps below:

Step 1: The monotone missing pattern is induced by Markov Chain Monte Carlo (MCMC) method in MI procedure. The monotone missing pattern means that if a patient has missing value for a variable at a visit, then the values at all subsequent visits for the same variable are all missing for the patient.

Step 2: The missing data at subsequent visits will be imputed using the regression method for the monotone pattern with adjustment for covariates including treatment groups, and baseline SDI score.

Data of each of the 50 complete datasets will be analyzed using an analysis of covariance (ANCOVA) model with treatment group as fixed effect, and the baseline SDI value as continuous covariate. SAS MIANALYZE procedure will be used to generate valid statistical inferences by combining results from these multiple analyses using Rubin's formula.

The imputation model will include:

- The covariates included in the ANCOVA model, including the treatment group and the baseline SDI value.
- Observed efficacy values from every clinic visit up to week 10

The ANCOVA model will provide least-squares means at week 10, and at other time points for each treatment group, with the corresponding standard error, confidence interval, and the p-value for treatment comparisons. The graph of LS-mean  $\pm$  SE by visit will be provided.

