## 2. INVESTIGATIONAL PLAN

### 2.1. Study Design and Randomization

This is a phase 2, multicenter, double-blind, randomized, placebo-controlled study investigating the efficacy, safety, tolerability, PK, and immunogenicity of dupilumab in adult patients with EoE. Patients will be randomized in a 1:1 ratio to receive SC 600 mg dupilumab or SC placebo loading dose followed by weekly SC 300 mg dupilumab or SC placebo during the 12-week double-blind treatment phase. The randomization will be stratified by baseline Straumann Dysphagia Instrument (SDI) PRO score ( $\geq 5$  and  $\leq 7$  versus  $> 7$ ).

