### 2.2. Sample Size and Power Considerations

The sample size calculations are based on the change from baseline in SDI score to week 12. The study of Straumann 2010 has a 2-week treatment period and the 3-point improvement from baseline is observed at end of week 2. A 3-point improvement from baseline is assumed for the study at both week 10 and week 12, so the power calculation for change from baseline in SDI score to week 12 is the same as the one at week 10. In the Straumann adult study, change from baseline in SDI score for active and placebo treatment group are -3.39 (2.46) [mean (maximum possible SD)] and -0.61 (2.19) [mean (maximum possible SD)] respectively.

A sample size of 18 patients per treatment arm will provide 94% power to detect a treatment effect, with an expected mean difference of 3 points in change from baseline to week 12 in SDI score between dupilumab and placebo at a 2-sided t-test with 5% significance level and an assumed SD of 2.46. Taking into account the assumed 15% dropouts, 22 patients per treatment arm will be enrolled.

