### **5.7.3. Analyses of Secondary Efficacy Variables**

The continuous secondary efficacy endpoints listed in Section 4.4.2 will be analyzed using the same approach as that used for the analysis of the primary endpoints. Inside step 2 of MI procedure, the missing data at subsequent visits will be imputed using the regression method for the monotone pattern with adjustment for covariates including treatment groups, baseline SDI score and relevant baseline value. Data of each of the 50 complete datasets will be analyzed using an analysis of covariance (ANCOVA) model with treatment group as fixed effect, and the baseline SDI value and relevant baseline value as continuous covariates.

Due to the substantial imbalance at baseline in the number of patients in the two randomization strata (only 12.8% patients in the strata of baseline SDI > 7), the imputation and ANCOVA will not use randomization strata as a factor. Instead the model includes the baseline SDI score as a continuous covariate.

Categorical analyses will be performed on responder data. Comparisons between dupilumab and placebo will be done using the Fisher exact test. Patients with early withdrawals or use of rescue medication or procedure will be counted as non-responders.

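### The pooled multiple-imputation tests have no stated degrees of freedom; Rubin's formula applied as written gives a nearly normal reference in about 40 patients and slightly too narrow intervals

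*SAP*

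**What the plan says.** For the primary endpoint, SAP section 5.7.2 plans that "Missing data from the FAS will be imputed 50 times to generate 50 complete data sets by using the SAS procedure MI". Each completed data set is analysed by ANCOVA with treatment and baseline SDI, and the pooling step reads: "SAS MIANALYZE procedure will be used to generate valid statistical inferences by combining results from these multiple analyses using Rubin's formula".

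Section 5.7.3 uses the same approach for the continuous secondary endpoints and adds the endpoint's own baseline as a second covariate: "Data of each of the 50 complete datasets will be analyzed using an analysis of covariance (ANCOVA) model". Section 5.7.4 refers the exploratory endpoints back to the primary and secondary methods.

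No section says which degrees of freedom the pooled tests use. The SAP neither says that complete-data degrees of freedom are supplied to the procedure nor that they are omitted.

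The sample size in section 2.2, by contrast, was planned "at a 2-sided t-test with 5% significance level and an assumed SD of 2.46".

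**The concern.** Rubin's large-sample degrees of freedom depend only on the number of imputations and the share of variance due to missing data. They do not reflect how few patients each ANCOVA rests on, and they become very large when little is missing. In a trial of about 40 patients the pooled test then becomes in effect a z-test, although an ordinary ANCOVA on the same data would use a t distribution with about 40 degrees of freedom.

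Two things are at stake, both small. P-values and intervals from the imputation analyses would be slightly too favourable. Sensitivity analyses 2 to 4 in section 5.7.2 are single ANCOVAs that need no pooling and use ordinary residual degrees of freedom. A difference between them and the primary result could therefore come partly from the reference distribution and not from the handling of missing data, which is what they are meant to test.

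**Working it through.** **Inputs.** Two-sided 5% level, SD 2.46, difference of 3 points, 18 evaluable and 22 enrolled per arm (SAP 2.2); 1:1 allocation (2.1); m = 50 imputations (5.7.2); ANCOVA with 3 parameters for SDI change (intercept, treatment, baseline SDI; 5.7.2), and 4 for an endpoint with its own baseline as well (5.7.3); 12.8% of patients in the upper SDI stratum (5.7.2 and 5.7.3).

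**The plan's own figures.** The SAP states: "A sample size of 18 patients per treatment arm will provide 94% power to detect a treatment effect". Noncentrality = 3 / (2.46 × √(2/18)) = 3 / 0.82 = 3.66; on 34 degrees of freedom the power is 94.4%, as stated. Dropout: 18 / 0.85 = 21.2, so 22 per arm, as stated. Both reproduce. The planned total is 44.

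**How many patients.** 44 is planned enrolment. The 12.8% stratum share matches no whole count out of 44 (5/44 = 11.4%, 6/44 = 13.6%). Between 36 and 60 patients it fits only 5/39 or 6/47, so both are carried as a range.

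**Degrees of freedom.** Let B be the between-imputation variance, T the total variance and g = (1 + 1/m)B/T.

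- Rubin, large sample: ν = (m − 1)/g².
- Barnard-Rubin: ν* = 1/(1/ν + 1/ν_obs), with ν_obs = [(ν₀ + 1)/(ν₀ + 3)] × ν₀ × (1 − g), where ν₀ is the complete-data error degrees of freedom.

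With ν₀ = 44 − 4 = 40 and g = 0.05: ν = 49/0.0025 = 19,600; ν_obs = (41/43) × 40 × 0.95 = 36.2; ν* = 36.2. At g = 0.10 the two are 4,900 and 34.1. Even at g = 0.5 Rubin's value is 196, against 17.4.

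**Size of the effect with almost no missing data.** Compare 1.960 with the t quantile on N minus the number of parameters. The shortfall in interval width is 1 − 1.960/t, and the size is 2P(t > 1.960).

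| Patients | Parameters | df | t(0.975) | Interval too narrow by | Size of nominal 5% test |
|---|---|---|---|---|---|
| 39 | 4 | 35 | 2.030 | 3.5% | 5.80% |
| 44 | 4 | 40 | 2.021 | 3.0% | 5.70% |
| 47 | 4 | 43 | 2.017 | 2.8% | 5.65% |
| 44 | 3 (primary) | 41 | 2.020 | 3.0% | 5.68% |

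For scale, a pooled statistic of 2.00 gives p = 0.0455 on the normal reference and p = 0.0523 on 40 degrees of freedom.

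**Simulation.** Null trials with 44 patients, 4 parameters, normal errors, outcomes missing at random rates of 0% to 30%, imputation from the same covariates as the ANCOVA, m = 50, 20,000 trials per rate (Monte Carlo standard error √(0.05 × 0.95/20,000) = 0.15 percentage points).

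| Missing | Size, Rubin df | Size, Barnard-Rubin df |
|---|---|---|
| 0% | 5.5% | 4.7% |
| 5% | 5.6% | 4.8% |
| 10% | 5.9% | 5.0% |
| 15% | 5.6% | 4.7% |
| 30% | 5.6% | 4.6% |

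The formula suggests that the gap widens with missing information (for ν₀ = 41 at g = 0.3: 4.4% too narrow, 6.0% size). The simulated size does not grow in that way. It did not include the weekly SDI values that the primary imputation model uses.

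**The case against.** The strongest objection is that the SAP does not state an error. It names a procedure and a formula and is silent on one option, and such options often sit in programming specifications. A reader might infer that the plan leaves the complete-data degrees of freedom out. The text does not support that; it supports only that the rule is open and that the one formula it names does not use them.

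A reader might also infer that the problem is confined to endoscopy and histology, because section 4.4 ties the heavy data loss to the electronic diaries. That does not hold either. The pooling sentence stands in the primary analysis and governs SDI first. Nearly complete endoscopy data are plausible, but the SAP gives no rate, and values after rescue are also set to missing.

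Nor can 5.7% be called the trial's real error rate. It assumes normal errors and almost complete data. Percent change in eosinophil counts or a short ordinal sum such as the EREFS need not behave like that at this sample size, and the effect of heavier missing data on the SDI test has not been established.

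Finally, the consequence is small: 0.7 percentage points of size at 44 patients, in a proof-of-concept study that makes no multiplicity adjustment for secondary endpoints. All of this stands and limits the point. It does not remove it: the formula as written gives slightly too narrow intervals in a trial planned on a t-test.

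**Conclusion.** The point holds as a minor one, conditional on Rubin's formula being applied as written. The pooled tests of all continuous endpoints, the primary SDI test included, would then use a nearly normal reference where the four-parameter ANCOVA has 35 to 43 residual degrees of freedom (39 to 47 patients; 40 at the planned 44) and the three-parameter SDI model has one more.

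With little missing data and normal errors, intervals are about 3% too narrow (2.8% to 3.5%) and a nominal 5% test has a size of about 5.7% (5.65% to 5.8%). Only results close to the 5% boundary would read differently. With more missing data the degrees-of-freedom formula points to a larger gap, but the simulation shows no such growth, and the actual size need not be inflated.

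**What to change.** Add one sentence to section 5.7.2 and carry it into 5.7.3 and 5.7.4: MIANALYZE is run with the complete-data error degrees of freedom of each ANCOVA (number of patients analysed minus number of model parameters; the EDF option), so that the Barnard-Rubin small-sample degrees of freedom are used.

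The cost is that sentence and one procedure option; no new data or analyses are needed. The price in results is that p-values become slightly less favourable and that the test can be slightly conservative when much is missing (4.6% in the simulation at 30% missing). The rule should be fixed before unblinding.

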#### Sensitivity analyses

In addition to the MI method described previously, sensitivity analyses for the primary efficacy endpoint will be conducted as described below:

1. The sensitivity analysis will use MI method, followed by ANCOVA based on all observed data no matter if rescue medication is used.
2. This sensitivity analysis will use ANCOVA model. The efficacy data will be set to missing after rescue medication is used. The post-baseline last-observed-case-forward (LOCF) method will then be used to impute missing values.
3. This sensitivity analysis will use ANCOVA model. The efficacy data will be set to missing after rescue medication is used. The post-baseline worst observation carried forward (WOCF) method will then be used to impute missing values.
4. This sensitivity analysis will use ANCOVA model, including all observed data, no matter if rescue medication is used.

### **5.7.3. Analyses of Secondary Efficacy Variables**

The continuous secondary efficacy endpoints listed in Section 4.4.2 will be analyzed using the same approach as that used for the analysis of the primary endpoints. Inside step 2 of MI procedure, the missing data at subsequent visits will be imputed using the regression method for the monotone pattern with adjustment for covariates including treatment groups, baseline SDI score and relevant baseline value. Data of each of the 50 complete datasets will be analyzed using an analysis of covariance (ANCOVA) model with treatment group as fixed effect, and the baseline SDI value and relevant baseline value as continuous covariates.

Due to the substantial imbalance at baseline in the number of patients in the two randomization strata (only 12.8% patients in the strata of baseline SDI > 7), the imputation and ANCOVA will not use randomization strata as a factor. Instead the model includes the baseline SDI score as a continuous covariate.

Categorical analyses will be performed on responder data. Comparisons between dupilumab and placebo will be done using the Fisher exact test. Patients with early withdrawals or use of rescue medication or procedure will be counted as non-responders.

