### 4.3. Pre-treatment/ Concomitant Medications and Procedures

Medications/Procedures will be recorded from the day of informed consent until the EOS visit. Medications will be coded to the ATC level 2 (therapeutic main group) and ATC level 4 (chemical/therapeutic subgroup), according to the latest available version of WHO Drug Dictionary (WHODD) version Sep 2016 at the coding of CRO. Patients will be counted once in all ATC categories linked to the medication.

Pre-treatment medications/procedures: medications taken or procedures performed prior to administration of the first study drug.

Concomitant medications/procedures: medications taken or procedures performed following the first dose of study drug through the EOS visit.

Prohibited concomitant medications/procedures during week 12 treatment period Treatment with the following concomitant medications is prohibited:

- Medications used for the treatment of EoE .
- Allergen immunotherapy.
- Patients who are not using PPI in the 8 weeks prior to screening cannot start PPI therapy prior to EOT visit
- Treatment with a live (attenuated) vaccine
- Treatment with an investigational drug (other than dupilumab)

Treatment with the following concomitant procedures is prohibited:

- Major elective surgical procedures
- Esophageal dilation (considered rescue procedure)
- Diet change.

If medically necessary (eg, for treatment of intolerable EoE symptoms) patients may be rescued with a prohibited medication or procedure at the discretion of the investigator. Patients who receive rescue treatment with a prohibited medication or procedure through week 12 will be permanently discontinued from study drug.

Rescue treatments for EoE: Blinded adjudication of rescue treatments will be implemented before database locks by considering the type of medications. A predetermined algorithm for rescue medications listed in [Appendix 10.6](#) will be used to programmatically search the concomitant medications (CMs). The rescue CMs will be reviewed and adjudicated by the medical monitor in a blinded fashion.

All patients will complete the schedule of study visits and assessments whether or not they complete study treatment. Investigators should make every attempt to conduct efficacy and safety assessments immediately before administering any rescue treatment. An unscheduled visit may be used for this purpose if necessary.

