#### Endoscopy with Esophageal Biopsies

Esophageal biopsies will be obtained by endoscopy at the screening and week 12 visits. A total of 9 mucosal pinch biopsies will be collected at each time point from 3 esophageal regions: 3 proximal, 3 mid, and 3 distal. Two samples from each region will be used for the histology. To participate in the study, patients must have a peak intraepithelial eosinophil count  $\geq 15$  eos/hpf (400X) in at least 2 of the 3 esophageal regions sampled. Peak esophageal eos/hpf (400X) will be determined for each of the 3 esophageal regions (proximal, mid, and distal) and overall at each time point. Mean peak of esophageal eos/hpf (400X) will be calculated from the peak count at each of the 3 esophageal regions for each patient at each time point.

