## 10. APPENDIX

### 10.1. Summary of Statistical Analyses

#### Efficacy Analysis:

| Endpoint   | Analysis Population | Primary Statistical Method                              | Supportive/Sensitive Statistical Method   | Subgroup Analysis | Other Analyses |
|--|---------------------|---|---|-------------------|----------------|
| Change in the SDI score at week 10 from baseline | FAS                 | MI + ANCOVA   | MI+ANCOVA regardless of rescue, ANCOVA on LOCF, WOCF and OC, and primary efficacy analysis on PPS | Yes               | Line plot      |
| Secondary continuous variables                   | FAS                 | MI + ANCOVA   | NO  | No                | Line plot      |
| Categorical variables                            | FAS                 | Fisher exact test / define missing as treatment failure |   | No                | Histogram      |
|  |                     |   |   |                   |                |

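### For the continuous endoscopy endpoints, the imputation in SAP 5.7.3 as written adds nothing to an observed-case ANCOVA and ignores the SDI course before rescue

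*SAP*

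**What the plan says.** SAP 4.4.2, on endoscopy, states: "Esophageal biopsies will be obtained by endoscopy at the screening and week 12 visits". EREFS and distensibility are recorded at the same procedure. The schedule in Appendix 10.2 adds an endoscopy at the early termination visit, and the window table in 6.4 maps early termination and unscheduled endoscopies on days 2 to 99 to week 12. No intermediate endoscopy is scheduled.

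Under 5.7.2, patients' "efficacy data through week 12 after rescue medication usage will be set to missing first" and are then imputed. Section 4.3 describes when rescue occurs: "If medically necessary (eg, for treatment of intolerable EoE symptoms) patients may be rescued". SDI is completed weekly from screening onwards.

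Section 5.7.3 applies the primary approach to the continuous secondary endpoints. Step 2 of the imputation is the "regression method for the monotone pattern with adjustment for covariates including treatment groups, baseline SDI score and relevant baseline value", and the ANCOVA has "treatment group as fixed effect, and the baseline SDI value and relevant baseline value as continuous covariates". Section 5.7.4 extends these methods to the exploratory endpoints. The only post-baseline content in the primary imputation model is "Observed efficacy values from every clinic visit up to week 10". The monotone pattern is defined within one variable: after a missing visit, "then the values at all subsequent visits for the same variable are all missing for the patient".

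In Appendix 10.1, the row "Secondary continuous variables" has NO under supportive or sensitivity methods. Exploratory endpoints have no row of their own.

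**The concern.** Multiple imputation helps over an observed-case analysis when the imputation model holds information that the analysis model does not. For SDI it does, because earlier weekly scores predict the missing later ones. For an endoscopy endpoint there is no earlier post-baseline value of the same variable, and the covariates named in 5.7.3 are exactly those of the ANCOVA. A patient whose endoscopy is missing or set aside after rescue is then imputed as a typical patient of the same arm and baseline who had an endoscopy without prior rescue.

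If rescued patients were doing worse, that is too favourable to the arm with more rescue. The weekly SDI that would show the worsening is collected but not named in the model. At stake are percent change in peak eos/hpf, the only secondary efficacy endpoint for the eosinophil objective; EREFS; and the exploratory mean eosinophil count, histology score and distensibility.

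**Working it through.** **1. The plan's own figures.** SAP 2.2 assumes a difference of 3 points, SD 2.46, two-sided 5% and 18 per arm. The noncentrality is 3 / (2.46 × √(2/18)) = 3 / 0.82 = 3.66 on 34 degrees of freedom. Power is 94.4%, against 94% stated. With 15% dropout, 18 / 0.85 = 21.2, so 22 per arm. Both reproduce. They supply the sample size used below and one scale for the effect, 3 / 2.46 = 1.22 SD.

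**2. Why the imputation adds nothing.** Let X hold the intercept, treatment, baseline SDI and the endpoint's baseline; subscript o marks observed patients and m missing ones; b is the observed-case ANCOVA estimate. The expected imputed value for missing patients is X_m b. The ANCOVA on completed data then averages

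(X′X)⁻¹ (X_o′y_o + X_m′X_m b) = (X′X)⁻¹ (X_o′X_o + X_m′X_m) b = b,

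because X_o′y_o = X_o′X_o b. So the pooled estimate equals the observed-case estimate, apart from the noise of 50 draws. For percent change this is exact only if the percent change itself is imputed; if the raw count is imputed, it is approximate.

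Numerical check on one simulated data set with 22 per arm:

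| Analysis | Estimate |
|---|---|
| Observed-case ANCOVA | -1.2139 |
| Imputation, 50 draws | -1.2011 |
| Imputation, 20,000 draws | -1.2133 |

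Over all scenarios in step 3, the mean estimates differed by at most 0.001.

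**3. Bias when SDI drives rescue, SDI taken at one common time.** Assumptions, none from the SAP: true effect -1 residual SD, 22 per arm, 500 trials per scenario, rescue more likely with worse SDI, residual correlation ρ between SDI and outcome, and every rescued patient's outcome missing.

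| ρ | Rescue, placebo v dupilumab | Full data | Imputation as written | With SDI added | Bias as written |
|---|---|---|---|---|---|
| 0.5 | 15% v 15% | -1.021 | -1.010 | -1.017 | 0.011/1.021 = 1% |
| 0.3 | 25% v 5% | -1.027 | -0.961 | -1.037 | 0.066/1.027 = 6% |
| 0.5 | 25% v 5% | -1.019 | -0.885 | -1.028 | 0.134/1.019 = 13% |
| 0.7 | 40% v 10% | -0.989 | -0.720 | -0.989 | 0.269/0.989 = 27% |

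At ρ = 0 all estimates agree within about 0.02.

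A large-sample check uses a rescued fraction f on placebo only, taken strictly as the worst SDI scores. The retained mean shifts by ρ φ(z_f)/(1 − f). At f = 0.15 and ρ = 0.5, with φ(1.036) = 0.233, this is 0.5 × 0.233 / 0.85 = 0.137 SD, or 0.137 / 1.22 = 11.2% of the effect.

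**4. Rescue spread over weeks 3 to 9.** The last SDI before rescue is then further from week 12, and the bias is smaller. With ρ of 0.5 to 0.7 and rescue from 15% v 0% to 40% v 10%, it is about 5% to 16% of the effect. A separate run at 15% v 0%, ρ = 0.5 and a weekly residual correlation of 0.8 gave 4.0%.

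**5. Which SDI value to add.** Using the last pre-rescue SDI for rescued patients and the week-10 SDI for the others turned that 5% to 16% understatement into a 5% to 8% overstatement, and created about 3% bias at equal rescue rates. Using week-10 SDI for everyone, observed or imputed, kept bias at about 1% or less.

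**The case against.** A reader might infer that these endpoints are analysed only in never-rescued completers. The SAP does not support that. Early termination and unscheduled endoscopies count for week 12, and 4.3 asks investigators to attempt assessments just before rescue. The group is patients with an endoscopy before any rescue. The simulations delete every rescued patient's outcome, so they lean towards a larger bias.

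A reader might also infer that nothing planned would reveal the problem. The proportion below 1 eos/hpf at week 12 counts rescue and missing data as failure, and rescue use is itself a reported secondary endpoint. These are partial checks: they do not correct the continuous estimates, and EREFS and distensibility have no such responder analysis.

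Nor is all rescue symptom-driven. Section 4.3 gives symptoms as an example, and Appendix 10.6 flags drug classes that may be taken for other conditions, subject to blinded adjudication.

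The wording leaves some room: the observed efficacy values in 5.7.2 are not tied to one variable, and the covariate list in 5.7.3 is introduced by 'including'. However, 5.7.3 names only baseline terms and the monotone definition stays within a variable. If SDI was intended, the SAP should say so.

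Finally, the size is assumed. The 15% in 2.2 is dropout, not rescue; the 1.22 SD effect belongs to SDI; and ρ is unknown. These are unadjusted endpoints in a proof-of-concept trial, and more rescue on placebo makes the result conservative. All of this stands and limits the weight of the point. It does not touch the equality in step 2.

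**Conclusion.** The structural point holds from the text: for the continuous endoscopy endpoints, the imputation as written is the observed-case ANCOVA plus noise. Bias follows only if rescue tracks symptoms, differs between arms, and SDI is related to the endoscopic outcome given baseline. Under the stated assumptions, with rescue at weeks 3 to 9, it is about 5% to 16% of the effect. More rescue on placebo understates the effect, more on dupilumab overstates it, and equal rates largely cancel. The SAP gives no rescue rate or correlation, so the actual size is unknown. This is a cheap improvement that uses data already collected, not a flaw that invalidates the analysis.

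**What to change.** In 5.7.3, for the week-12 endoscopy endpoints (and through 5.7.4 the exploratory ones), add post-baseline SDI at a common time point to the step 2 regression. This is each patient's week-10 SDI, observed or as imputed in the same imputation cycle from the SDI values before rescue or withdrawal. Do not mix last pre-rescue scores with week-10 scores. Leave the ANCOVA unchanged. State whether percent change or the raw value is imputed.

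In Appendix 10.1, replace NO for these endpoints with one supportive run using all observed week-12 endoscopies regardless of rescue, as sensitivity analysis 1 in 5.7.2 does for SDI. Section 2.3 asks rescued patients to return for remaining visits, so such endoscopies may exist.

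The cost is SAP wording and a few lines of code, with no new data. The imputation model gains one parameter and depends on diary completeness, which 4.4 reports as poor at week 12; week 10 was chosen because more data are available. Precision changes little: with SDI at one common time, ρ = 0.5 and 25% v 5% rescued, the standard error rose from 0.337 to 0.346.
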